Total intravenous anesthesia (TIVA) and balanced inhaled anesthesia (BIA) are current techniques used nearly interchangeably for the maintenance of anesthesia during various surgical procedures, including herniorrhaphy surgery. Research evidence supports that reduced intraoperative stress hormone levels result from the use of TIVA versus BIA. There is also data to support that an increased level of intraoperative stress hormones leads to an increased pain score postoperatively. The primary aim of this study is to determine the effect of TIVA versus BIA in the incidence of CNP following herniorrhaphy surgery. No studies currently exist in the literature demonstrating a link between physician-selected general anesthetic technique and the incidence of CNP.

Hypothesis

In patients undergoing herniorrhaphy, a TIVA anesthetic protocol will result in a lower incidence of acute and chronic neuropathic pain (ANP and CNP, respectively) than a BIA anesthetic protocol.

Secondary Aims

For each anesthetic protocol: [i] the proportion of patients experiencing ANP; [ii] the proportion of ANP patients developing and not developing CNP; [iii] the rate of CNP given ANP; [iv] and a comparative analysis of the postoperative pain scores will also be performed, testing the link between anesthetic technique and acute pain, as well as ANP's connection to CNP. Additionally, data regarding the intraoperative stress response will be collected in an attempt to replicate the findings that TIVA results in lower intraoperative stress levels than BIA.

4.0 * Provide a summary of the background of the study, and explain how this research will contribute to existing knowledge. Describe previous studies that provides a basis to show that the proposed research can be carried out without undue risk to human subjects.

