It has long been known that chronic pain is a common negative outcome following hernia repair and its sufferers often frequent pain clinics. Estimates of the incidence of chronic pain following herniorrhaphy range from 10%(1) to as high as 63% at 12 months after surgery.(2) Despite the improved immediate pain outcomes with laparoscopic techniques, a chronic pain incidence of 15% has been found at 9 months after the procedure.(3) CNP causes a burden to the patient and the healthcare system. In a study of thoracic surgery, Searle et al demonstrated that ANP is predictive of CNP with a 3.5 times increased relative risk in patients who experience ANP in the postoperative period, as measured by the Leeds Assessment of Neuropathic Symptoms and Signs (LANSS) scale. However, ANP is not the only factor that determines CNP as demonstrated in the same study of thoracic surgery in which 8% of patients developed ANP while a far greater 22% experience CNP at 3 months(4).

The factors predisposing a patient to CNP may begin even before incision. The body mounts a stress response in reaction to perioperative surgical noxious stimulation including but not limited to intubation, incision, maximum surgical stimulation, and extubation with activation of the sympathetic nervous system and release of stress hormones including epinephrine, norepinephrine, cortisol, and ACTH.(5) The goal of anesthesia and analgesia is to reduce this stress response and suppress pain pathways. However, choice of anesthetic may influence intraoperative stress response with increased sympathetic outflow seen when using balanced inhaled anesthesia (BIA) maintained with sevoflurane versus a total intravenous anesthetic maintained with propofol (TIVA).(6) The use of perioperative intravenous ketamine and lidocaine are other anesthetic modifications demonstrating an attenuated surgical stress response with smaller increases in heart rate and blood pressure as well as decreased plasma cortisol levels.(7)

Studies have shown that increased intraoperative stress hormone activation is related to increased pain perception in the postoperative period.(8) If intraoperative stress hormone activation can be attenuated by anesthetic technique, it would provide support for an existing standard of care method to reduce acute and chronic neuropathic pain in postoperative patients.

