The initial data will also consist of baseline measurements of the outcome variables to establish baseline values. These will consist of the study's primary endpoints: the pain numerical rating scale (NRS, the traditional 0-10 pain score where 0 indicates no pain and 10 equates to the most intense pain imaginable), and the revised version of the short form McGill Pain Questionnaire. Additionally, the study's secondary endpoints will be collected: the self-report of the Leeds Assessment of Neuropathic Symptoms & Signs (s-LANSS), and the Pain Quality Assessment Scale (PQAS). The NRS is being used as it will allow us to compare our results with those of historical studies that only used this numerical score. Additionally, in the initial post-operative assessment, it is believed that subjects will not have yet recovered the mental faculties necessary for the more involved scales. The revised short form McGill Pain Score Questionnaire (sf-MPQ-2) is considered by many to be the "gold standard" pain questionnaire, especially for neuropathic pain. The s-LANSS has been shown to discriminate neuropathic from non-neuropathic pain; a score of greater than 12 is considered to be indicative of neuropathic pain (4). Finally, research has shown that the PQAS is able to assess pain changes during and as a result of treatment.

Intra-operative data recorded will include the total amounts of all medications documented on the Anesthesia Record, the surgical approach used (laparoscopic versus open), the type and location of the hernia being repaired, and details on any local anesthetic infusions used by the surgery team.

Follow-up data will be collected at six time points in person or over the phone per convenience including a) post-operative prior to Post Anesthesia Recovery Unit discharge, b) 18-36 hours post-operative, c) 1 months post-operative, d) 3 months post-operative, e) 6 months post-operative, and f) 12 months post-operative. Additional data collected will include details about analgesic use at all time points.

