The primary outcome is the overall incidence of CNP and will be compared across the three arms: TIVA-R, TIVA-K, and BIA protocol. This is a pilot study, as direct numbers for the estimation of the sample size are not available, given the varied incidence of chronic pain (10 to 63%) found in the literature, and the fact that anesthetic technique is typically not presented with this data. Because our hypothesis is that technique will affect CNP through the anesthetic technique's effect on the surgical stress response, we reviewed the literature surrounding this phenomenon. Significant differences in the circulating catecholamine concentration and in heart rate variability patterns has been observed in a study comparing BIA to TIVA (without specifying if ketamine or remifentanil were used) with 43 patients(6). The link between intraoperative stress and acute (24 hour postoperative) pain was demonstrated in a study of 34 subjects(11) using heart rate variability as a measure of stress, and in a study of 45 subjects using serum catecholamines(8). While this provides little guidance for technique's effect on chronic pain, it provides a starting point for pilot work. Therefore, we are targeting 48 patients, 16 in each group. Subject recruitment numbers will be closely monitored, and the randomization technique may be modified as the study nears completion to ensure balanced groups.

The surgical details and demographic data for each patient will be recorded on the data collection forms. This information will then be de-identified and entered into SPSS (v.21, SPSS, Inc., Chicago, IL.). SPSS is a program that performs statistical calculations. It resembles Microsoft Excel in terms of layout but is able to handle the advanced calculations required for statistical analysis.

Categorical data (demographics) will be tested with a Fisher's exact test (for 2x2 tables) or a Chi-square, both with two-sided tails. Continuous variables will be compared with a two-sample t-test. An overall p-value of 0.05 with Bonferroni or other relevant correction for multiple comparisons will be used for significance. If any of these vary significantly between the groups, multivariate techniques will be used instead of the univariate approach described below.

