All outcome variables (NRS, s-LANSS, PQAS, sf-MPQ) are ordinal data, and as such will require non-parametric testing. As the study is progressing, the techniques will be compared via Kruskal-Wallis testing at each time interval. The presence of CNP will be defined as a positive S-LANSS (scores ≥ 12 are highly suggestive of neuropathic pain); after the 3 month time point will be considered "chronic". These definitions are consistent with the literature and with published standards.(2,4) Thus, for the 6 and 12 month time points, the incidence of CNP for each technique will be computed and compared via chi-squared analysis.

Interim analyses are planned for 3, 6, 9 and 12 months, with the major focus being a definitive power analysis for variables found to be non-significant (as this is a pilot study). Because this study involves no changes to standard of care for herniorrhaphy surgery patients, stopping the study prematurely based on these interim analyses is not expected.

As planned, a continuous sampling of patients undergoing umbilical or inguinal herniorrhaphy will be included in this study. In addition, all equipment and personal required for this study are already in place within the VAPHS. Therefore, time for patient enrollment or equipment procurement is not necessary, and this study can begin as soon as all approvals (including IRB, R&D and ACOS) are granted. The study will continue for at least 1 year. The decision to continue past this time will be based on the achieved statistical power after 12 months of data collection. Because the data will be entered throughout the year and analyzed at 3 month

intervals, the time required for final analysis will be minimal. Submission for publication is expected within 3 to 12 months of the completion of data collection.

ID: Pro00000878

View: 5 Sub-Studies

1.0 * Is there a sub-study or are there sub-studies associated with this study?
There is no sub-study associated with this study.

ID: Pro00000878

View: 6 Study Population Summary

Study Population Summary

1.0 * What is the maximum number of subjects you plan to enroll at VAPHS?
60

2.0 * Do you plan on enrolling patients into different categories:
 Yes **No**

If yes, please explain:

3.0 If this is a multi-site study, indicate the projected total subject accrual:

4.0 * Please provide a justification for the sample size:

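### The secondary aims promise to test whether ANP is connected to CNP, but no listed analysis compares CNP between patients with and without ANP, and the per-arm rate listed instead will be very sparse

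*Combined protocol and SAP*

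**What the plan says.** View 2, 3.0 (Secondary Aims) lists four items for each anesthetic protocol. Item [i] is the proportion with ANP, items [ii] and [iii] are "ii] the proportion of ANP patients developing and not developing CNP; [iii] the rate of CNP given ANP", and item [iv] is a comparison of postoperative pain scores. The same sentence gives the purpose as "testing the link between anesthetic technique and acute pain, as well as ANP's connection to CNP".

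View 4.1 (analysis plan) compares the pain scales between techniques by Kruskal-Wallis test at each time point. It defines CNP by a positive s-LANSS and compares CNP incidence between techniques by chi-squared test at 6 and 12 months. It does not mention ANP. On size it says: "Therefore, we are targeting 48 patients, 16 in each group". View 6, 1.0 sets a maximum of 60, and the study is described as a pilot.

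The background (View 2, 4.0) cites a thoracic-surgery study in which "8% of patients developed ANP while a far greater 22% experience CNP at 3 months", with a "3.5 times increased relative risk in patients who experience ANP in the postoperative period".

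Three places bear on how ANP would be defined:
- View 0.0, 2.0 counts the PACU, 24-hour and 1-month assessments as acute.
- View 4 (Data Collection) says of the first post-operative assessment that "it is believed that subjects will not have yet recovered the mental faculties necessary for the more involved scales", whereas the abstract (View 2, 2.0) plans every scale in the PACU.
- View 4 puts the s-LANSS cutoff for neuropathic pain above 12, and View 4.1 puts it at 12 or more.

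**The concern.** A connection between ANP and CNP is a contrast: P(CNP | ANP) against P(CNP | no ANP). The relative risk of 3.5 cited in the background is a contrast of this kind. Items [ii] and [iii] both give the first term, and no listed item gives the second. A team following the text would report, for each arm, a proportion with a denominator of perhaps one or two, and would have made no comparison that bears on the stated aim.

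This matters because the pilot is meant to be the foundation for a larger study (View 7.1), and a usable estimate of the ANP-CNP link is one thing it could supply. Because the plan does not say which acute assessment defines ANP, that choice could also be made after the data are seen.

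**Working it through.** **Plan's own figure.** 3 × 16 = 48 agrees with the stated target. No effect size, event rate or power is given for it, so there is no sample-size calculation to reproduce.

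**Inputs.** n = 16 per arm (View 4.1). ANP 8%, CNP 22% and relative risk 3.5 come from the thoracic-surgery study in View 2, 4.0. The documents give no ANP rate for hernia repair, so 8% is an assumption, and 15%, 20% and 30% are assumed alternatives. Chronic pain incidence is described as "given the varied incidence of chronic pain (10 to 63%) found in the literature".

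**Sparsity of the per-arm rate.** Expected ANP patients per arm = 16a, where a is the ANP rate. P(no ANP patient in a given arm) = (1 − a)^16. P(at least one of three arms has none) = 1 − [1 − (1 − a)^16]³.

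| ANP rate | Expected per arm | P(given arm has none) | P(some arm has none) |
|---|---|---|---|
| 8% | 1.28 | 0.263 | 60% |
| 15% | 2.4 | 0.074 | 21% |
| 20% | 3.2 | 0.028 | 8% |
| 30% | 4.8 | 0.003 | 1% |

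At the maximum of 60 (20 per arm if equal) and 8% ANP, 1.6 are expected per arm and the last probability is 47%. An arm with no ANP patient has an undefined rate. With few, the Clopper-Pearson 95% interval is almost uninformative: 2.5% to 100% for 1 of 1, and 1.3% to 98.7% for 1 of 2.

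**Where the CNP cases would lie.** Using the three thoracic figures together, CNP risk without ANP = 0.22 / (0.92 + 3.5 × 0.08) = 0.22 / 1.20 = 0.183, and with ANP 3.5 × 0.183 = 0.642. The share of CNP cases without ANP = 0.92 × 0.183 / 0.22 = 0.77. On these assumptions, about 77% of CNP cases fall outside items [ii] and [iii].

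**What a pooled comparison could show.** Over 48 patients at 8% ANP, 48 × 0.08 = 3.84 with ANP and 44.16 without are expected. Power of a two-sided Fisher test at 0.05, at relative risk 3.5, was enumerated over the random number of ANP patients:

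| ANP rate | CNP overall | Power, 48 patients |
|---|---|---|
| 8% | 10% | 17% |
| 8% | 15% | 26% |
| 8% | 22% | 39% |
| 15% | 22% | 55% |
| 22% | 22% | 60% |
| 30% | 22% | 59% |

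At 8% ANP and 22% CNP, power is about 50% with 60 patients and about 8% within a single arm of 16. At 8% ANP, a relative risk of 3.5 cannot hold once overall CNP exceeds 1.20 / 3.5 = 34%, because the risk with ANP would pass 1. The upper part of the 10% to 63% range is therefore incompatible with that pair of assumptions. No dropout or multiplicity correction is applied, so these powers are optimistic.

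**The case against.** The strongest reply is that the comparator is not lost. The s-LANSS is planned for all patients, item [i] gives P(ANP), item [iii] gives P(CNP | ANP), and the primary outcome gives overall CNP. With a common time point and complete data, P(CNP | no ANP) = [P(CNP) − P(CNP | ANP) × P(ANP)] / [1 − P(ANP)]. This is correct, and it is why the gap lies in the listed analysis and not in the data. But no section commits to deriving, pooling or comparing that rate.

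A second reply is that the phrase about testing follows item [iv] and may refer to it. The sentence can be read that way, but item [iv] concerns pain scores, and View 4.1 compares those by technique, not by ANP status.

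A third is that this is a pilot, where imprecise secondary results are expected. That excuses low power but does not supply a missing contrast.

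A reader might also infer that the trial will test CNP-given-ANP between arms, which would condition on an event that technique may alter after randomisation. The documents state no such test: [ii] and [iii] are per-arm quantities only. Nor do the documents establish that each arm will have about one ANP patient. That rests on one rate from another operation, and counting ANP at any acute visit, including 1 month, could give a higher rate than a single visit.

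**Conclusion.** The concern holds for the analysis as listed. The secondary aims promise a test of the ANP-CNP connection, yet the listed quantities give only P(CNP | ANP), twice, and the analysis plan compares techniques only. This structural point does not depend on any event rate.

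The sparsity of the per-arm rate does. It is severe at 8% ANP (1.3 patients per arm, 60% chance of an empty arm) and eases to 4.8 per arm and 1% at 30%. None of these rates is known for hernia repair.

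Two stronger readings fail. The aim is not unanswerable, because the planned data contain the comparison. Nor would pooling settle the question: power at relative risk 3.5 stays between about 17% and 60% over the settings shown, before dropout or multiplicity correction. The pooled analysis estimates the link and should be presented that way. Since this is a secondary aim in a pilot and the remedy needs no new data, it should be corrected but does not threaten the primary comparison.

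**What to change.** - Replace [ii] and [iii] with one exploratory comparison of CNP incidence in patients with and without ANP, pooled over the three arms. Report the risk ratio and risk difference with exact 95% intervals.
- Add an arm-stratified estimate as a sensitivity analysis only, since an arm with no ANP patient contributes nothing to it.
- Give the ANP-by-CNP table for each arm as counts.
- State in advance which acute s-LANSS assessment or assessments define ANP. Reconcile View 0.0, where PACU, 24 hours and 1 month are all acute, with the doubt in View 4 about the longer scales at the first post-operative assessment.
- Reconcile the s-LANSS cutoff (above 12 in View 4, 12 or more in View 4.1) and use the same one for ANP and CNP.
- Label the result as estimation, not a definitive test, and give the power range above with its assumptions.

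The cost is analysis-plan wording; no visit, scale or patient is added. The downside is that the per-arm rates of CNP given ANP become descriptive.

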The objective of this study is to determine if incidence of chronic neuropathic pain (CNP) varies as a function of anesthetic technique in patients undergoing inguinal herniorrhaphy surgery at VAPHS, hypothesizing that a total intravenous anesthetic (TIVA) protocol utilizing propofol and lidocaine will result in a lower incidence of acute and chronic neuropathic pain (ANP and CNP, respectively) than an inhalational anesthetic based protocol.

This is a patient-blinded, prospective, randomized study. Forty-eight patients undergoing either inguinal (including femoral) or ventral (including umbilical) herniorrhaphy that requires general anesthesia in the operating room will be enrolled. Exclusion criteria include: those unable to communicate directly with the investigators, a history of disease that prevents anesthetic randomization, the presence of any pain-related disorders such as fibromyalgia, and the need for emergency surgery. Patients will be assigned to one of three anesthetic technique protocols: TIVA with ketamine (TIVA-K), TIVA with remifentanil (TIVA-R), or Balanced Inhalational Anesthesia (BIA, consisting of an inhaled anesthetic only) using a computer-generated random numbers table. Sixteen subjects will be used in each group.

The medications administered in the operative room will be recorded. Study data will include the pain numerical rating scale (NRS, the traditional 0-10 pain score where 0 indicates no pain and 10 equates to the most intense pain imaginable) at rest and with movement, the revised version of the short form McGill Pain Questionnaire (sf-MPQ), the self-report of the Leeds Assessment of Neuropathic Symptoms & Signs (s-LANSS), and the Pain Quality Assessment Scale (PQAS). These will be collected during the pre-operative assessment, in the PACU prior to discharge, approximately 24 hours post-operative, 1 months post-operative, 3 months post-operative, 6 months post-operative, and 12 months post-operative.

3.0 * Describe the study objectives. Please include primary aim and hypothesis, if applicable any secondary aims and hypotheses.**Objective and Specific Aims**

To determine if incidence of chronic neuropathic pain (CNP) varies as a function of anesthetic technique in patients undergoing inguinal herniorrhaphy surgery at VAPHS.

Primary Aim

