A total of 48 patients undergoing either inguinal (including femoral) or ventral (including umbilical) herniorrhaphy that requires general anesthesia in the operating room will be enrolled in the study with continuous sampling beginning as soon as the protocol is approved. Inguinal hernias will be the focus, as they are thought to have a higher incidence of chronic pain; however, ventral herniorrhaphy may also be used if required to meet study goal numbers. A patient will be considered enrolled in the study when they have passed initial screening questions, signed the consent form, and been randomized to one of three anesthetic technique protocols (TIVA-K, TIVA-R, or BIA). 16 subjects will be used in each group. At the time of first subject enrollment, the subjects will be divided amongst the three groups using a random assignment table generator (www.graphpad.com/quickcalcs/randomize2) stating that A will equal TIVA-K, B will equal TIVA-R, and C will equal BIA. The results will be recorded and followed for all subsequently enrolled patients.

Consistent with our current standard of care, all protocols will begin with perphenazine (up to 8 mg) and acetaminophen (up to 1300 mg) by mouth in the pre-operative holding area, and premedication prior to induction with up to 2 mg of midazolam.

The TIVA-K protocol will consist of the induction of anesthesia with propofol (1-2.5 mg/kg) and ketamine (20 mg), with muscle relaxation being accomplished with either succinylcholine or rocuronium as necessary. Endotracheal intubation may be used for airway management. Anesthesia will be maintained with a propofol infusion (50-150 mcg/kg/min), lidocaine infusion (0.5-1 mg/kg/hr), and ketamine (5 mg each half hour to a maximum of 50 mg). Standard antiemetic medications will be given.

The TIVA-R protocol will consist of the induction of anesthesia with propofol bolus (1-2.5 mg/kg) and the initiation of a remifentanil infusion (0.05-2 mcg/kg/min). Muscle relaxation will be accomplished with either succinylcholine or rocuronium as necessary. Endotracheal intubation may be used for airway management. Anesthesia will be maintained with a propofol infusion (50-150 mcg/kg/min), lidocaine infusion (0.5-1 mg/kg/hr), and continuation of the remifentanil infusion (0.05-2 mcg/kg/min). Standard antiemetic medications will be given.

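### The objective names inguinal repair, but ventral repairs may be enrolled without a cap, and the planned chronic neuropathic pain comparison does not account for hernia type

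*Combined protocol and SAP*

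**What the plan says.** **Population.** The objective in View 2 (abstract and item 3.0) asks whether CNP incidence "varies as a function of anesthetic technique in patients undergoing inguinal herniorrhaphy surgery at VAPHS". The brief description in View 0.0 also refers to inguinal repair. The hypothesis in View 2 is wider and names no type: "In patients undergoing herniorrhaphy, a TIVA anesthetic protocol will result in a lower incidence". The inclusion criterion in View 6.1 takes any herniorrhaphy under general anesthesia. The enrolment text in Views 2, 4, 8 and 9.4 lists inguinal (with femoral) or ventral (with umbilical) repair.

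**Role of ventral repair.** View 4, item 1.0 says "Inguinal hernias will be the focus, as they are thought to have a higher incidence of chronic pain", and then that "ventral herniorrhaphy may also be used if required to meet study goal numbers". It sets no trigger, date or maximum. View 4.1 says that "a continuous sampling of patients undergoing umbilical or inguinal herniorrhaphy will be included in this study".

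**Use of hernia type.** The intra-operative data in View 4 include "the type and location of the hernia being repaired". The allocation described there is not stratified by it. View 4.1 compares CNP incidence by technique at 6 and 12 months with a chi-squared test and names no covariate, stratum or subgroup. An earlier paragraph of View 4.1 switches to multivariate methods if a tested variable differs significantly between groups. It describes the categorical variables to be tested as demographics, so it is unclear whether hernia type is one of them.

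**The concern.** The protocol names a factor that it expects to predict the primary outcome, records it, and then leaves it out of both the allocation and the specified primary comparison. Two things follow.

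- **Target population.** No planned analysis estimates CNP in inguinal patients alone, although that is the stated objective. The reported incidence would be an average over whatever mix of hernia types accrues. View 4.1 uses interim data for a definitive power analysis, and View 7.1 presents the trial as the foundation for a larger study, so an incidence from an uncontrolled mix would carry forward.
- **Comparison between arms.** With 16 patients per arm, hernia type can differ noticeably by chance. The only safeguard is a significance test, which has little power at this size.

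**Working it through.** **What can be reproduced.** The plan's only figure is the sample size: 3 × 16 = 48. No power, effect size or event rate lies behind it. The documents give chronic pain incidence as 10 to 63% overall, with no split by hernia type and no expected ventral share. All shares and type-specific rates below are therefore assumptions.

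**1. Does the imbalance test catch imbalances in hernia type?** For three arms of 16 and V ventral patients, the Pearson statistic is Σ(vᵢ − V/3)² × [1/(V/3) + 1/(16 − V/3)] on 2 df, and p = exp(−X²/2).

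- Split 8/4/4 (V = 16, mean 5.33): Σ = 7.11 + 1.78 + 1.78 = 10.67. X² = 10.67/5.33 + 10.67/10.67 = 3.0, so p = 0.22.
- Split 2/6/4 (V = 12, mean 4): Σ = 4 + 4 + 0 = 8. X² = 8/4 + 8/12 = 2.67, so p = 0.26.

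Exact enumeration of random allocations, with V fixed:

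| Ventral of 48 | Largest gap between arms ≥ 4 patients | Test significant at 0.05 | Share of those gaps missed |
|---|---|---|---|
| 8 | 23% | 3.5% | 85% |
| 12 | 32% | 5.8% | 82% |
| 16 | 40% | 3.8% | 91% |
| 24 | 43% | 7.7% | 82% |

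A gap of 4 patients is 25 points in ventral share. The test misses more than four in five such gaps. Any multiplicity correction, which View 4.1 allows, would make it stricter.

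**2. How far can an imbalance move the result?** Shift = gap in ventral share × difference in CNP rate between hernia types.

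- 30% inguinal v 10% ventral: 0.20 × 0.20 = 4 points.
- 63% v 10%, the ends of the range cited in View 4.1: 0.20 × 0.53 = 10.6 points.

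**3. Against what noise?** For a simple two-group yardstick, take pooled TIVA (32) against BIA (16). This is not the planned three-arm test. SE = √[p(1 − p)(1/16 + 1/32)].

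- 30% v 10%, 20% ventral: p = 0.8 × 0.30 + 0.2 × 0.10 = 0.26, SE = 13.4 points.
- 30% v 10%, 40% ventral: p = 0.22, SE = 12.7 points.
- 63% v 10%, 40% ventral: p = 0.418, SE = 15.1 points.

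On the same yardstick, a 20-point or larger imbalance has probability 9.6%, 14.7% or 17.6% at ventral shares of 20%, 30% or 40% (binomial enumeration).

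**4. How does the mix change incidence?** At 30% v 10%, a ventral share of 20 to 40% lowers overall incidence from 30% to between 26% and 22%. At 63% v 10%, it falls from 63% to between 52% and 42%.

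**5. Does stratifying help?** Simulated SD of the TIVA–BIA difference with no drug effect (200,000 runs), crude v Mantel-Haenszel:

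- 30% v 10%, 20% ventral: 13.4 v 13.4 points.
- 30% v 10%, 40% ventral: 12.7 v 12.5 points.
- 63% v 10%, 40% ventral: 15.1 v 13.0 points.

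Precision was not lost in these cases. The gain is negligible when the type-specific rates are close and useful when they are far apart.

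**The case against.** The strongest reply is that this is a declared pilot, that the hypothesis and the inclusion criterion already say herniorrhaphy without a type, and that randomization deals with hernia type on average. Chance imbalance is already within the test's error rate. At 30% v 10%, a 4-point shift is under a third of the standard error and stratifying gains almost nothing. All of that stands. It limits the size of the point, but it does not supply an estimate for the stated objective. Nor does it justify relying on a significance trigger for a factor that the protocol itself calls prognostic.

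A reader might infer three stronger claims, none of which the documents support.

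- **Ventral patients come late.** The wording about meeting goal numbers may suggest this, but no sequence is stated. Views 4 and 4.1 describe continuous sampling that covers both types.
- **Late allocation biases the result.** View 4.1 does say that "the randomization technique may be modified as the study nears completion to ensure balanced groups". Bias by hernia type would require ventral cases to cluster at the end, the option to be used, and the change to alter allocation at that time. None of these is stated.
- **Hernia type is ignored.** It is recorded, and the conditional multivariate step might reach it. The accurate statement is that no prespecified analysis accounts for it with certainty.

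**Conclusion.** The point holds in a limited form. The objective and lay summary do not match the enrolled population, and the specified CNP comparison does not account for hernia type except possibly through a weak, conditional step of unclear scope. With randomization intact, the consequences are chance imbalance, some loss of precision and an unclear target population, not systematic bias.

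The size depends on type-specific rates that the documents do not give. A 20-point imbalance is worth 4 points under a moderate assumption (30% v 10%) and about 11 points if hernia types differ across the whole cited range (63% v 10%), against a standard error of roughly 13 to 15 points on the two-group yardstick. The mismatch in population and the weakness of the trigger do not depend on those assumed rates.

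**What to change.** 1. Reword the objective (View 2) and the lay summary (View 0.0) to inguinal or ventral herniorrhaphy, to match eligibility.
2. In View 4.1, prespecify the three-arm CNP comparison stratified by hernia type (inguinal/femoral v ventral/umbilical), by an exact or Cochran-Mantel-Haenszel method, whatever the baseline test shows.
3. Report CNP by arm in inguinal patients alone beside it.

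This needs a wording change and one stratified analysis of data already collected, with no new patients or procedures. The downsides are a sparse ventral stratum, a smaller sample for the inguinal-only estimate (36 of 48 if 12 are ventral), and little gain in precision if CNP rates turn out similar across hernia types.
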